### **9.3.1. Primary outcome variable(s)**

- Date of death
- Time of TACE non-eligibility
- Time of decision to treat with Sorafenib

### **9.3.2. Secondary outcome variable(s)**

- Documented disease progression
- Response assessment to treatment
- Start and stop date of sorafenib treatment
- Assessments for liver function
- Documented Adverse Event

### **9.3.3. Demographic data and other baseline characteristics**

The following data will be recorded:

- birthdate (at least year)
- sex
- race (asian, white, black, other). Note: race will not be recorded in countries where legally not permitted.
- weight (kg / pound)
- height (cm / inch)
- alcohol use
- status of cigarettes smoking
- medical history of HCC
- history of liver disease
- general medical history

### **9.3.4. Laboratory data**

- platelets
- INR
- Total bilirubin
- ALT
- AST
- Alkaline phosphatase
- Creatinine
- Creatinine clearance
- Albumin
- Sodium
- LDH
- Alpha fetoprotein
- C reactive protein (baseline only)
- Gamma-Glutamyl-Transferase (GGT)

- Cholinesterase (ChE)

### **9.3.5. Pretreatment of HCC**

For patients that are not newly diagnosed, any systemic or non-systemic pretreatments will be documented.

### **9.3.6. Concomitant medication**

Information on concomitant medication (as defined in Section 6.2) to be collected includes:

- Trade name or INN
- Start date (at least year)
- Stop date or “continued”
- Daily dose, if applicable
- Indication: “treatment of HCC”, “treatment of concomitant disease”, “treatment of AE”

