### 9.3. Variables

The investigator collects historic data (demographic and clinical characteristics) from medical records if available, or else by interviewing the patient. Likewise, the investigator collects treatment related data during initial visit and follow-up visits.

Table 2: Tabulated overview on variables collected during the study

	Study Entry/ Initial visit	Follow-up visit	Last visit / End of observation
patient information and consent	X		
specialty of the investigator and previous physician(s)	X		
demographic data	X		
Current alcohol consumption	X		
etiology of underlying disease/findings	X		
past medical history and concomitant diseases	X		
date of initial HCC diagnosis	X		
Disease status at initial diagnosis (BCLC stage, TNM classification)	X		
previous treatments for HCC	X		
height	X		
smoking	X		
alcohol use	X		
visit date	X	X	X
blood pressure	X	X	
body weight	X	X	
Disease status (BCLC stage, TNM classification)	X	X	
Child-Pugh score	X	X	
performance status (ECOG)	X	X	
Tumor assessment *	X	X	
response evaluation compared to initial TACE		X	
response evaluation compared to most recent TACE		X	
response evaluation compared to initiation of sorafenib		X	
laboratory data	X	X	
Decision on further treatment**		X	
Details on TACE treatment (date, embolization agent, drug name)		X	
Details on sorafenib therapy (dates, daily dose, interruptions)		X	
Details on other systemic therapy for HCC		X	
Disease status summary**	X	X	
AE		X	X
concomitant medication (including non-systemic therapy for HCC)	X	X	X
Reasons for end of observation			X
physician's signature			X (one signature at the end of documentation)

\* The time interval between two documented tumor assessments is assumed to be 6 - 12 weeks, although this will be at the treating physician's discretion

\*\* Must be documented at each follow-up visit

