### **9.3.10. Exposure/treatment**

Information on TACE to be documented:

- Date of administration
- Embolization agent
- Drug name

Information on sorafenib to be documented:

- Start date of treatment
- Prescribed dose
- Frequency of daily intake
- Date and details on dose adaptations
- Dates and details on treatment interruptions
- Date of permanent stop of treatment
- Reason(s) for interruptions or stop of treatment

Information on other systemic treatments to be documented:

- Start date of treatment
- Drug name or tick for "investigational drug"
- Stop date of treatment

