#### **9.7.6. Analysis of safety data**

Adverse events will be summarized for the overall safety population and by cohort using the National Cancer Institute (NCI) Common Terminology Criteria Adverse Event CTCAE and the MedDRA coding system. Event rates for each adverse event, as well as drug related AEs and serious AEs, will also be summarized by NCI CTCAE grade for the overall safety population and by cohort.

Other safety parameters, including blood pressure, will be summarized descriptively.

AEs occurred during treatment for HCC also will be summarized for each treatment for HCC.

Subgroup analyses stratified with prognostic/predictive factors collected at baseline may be explored.

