## **11.2. Collection**

Starting with the first TACE, all non-serious Adverse Events (AE) must be documented on the AE Report Form or to the electronic CRF within 5 days of awareness. All serious AEs (SAE) must be documented immediately (within 24 hours of awareness).

For each AE/SAE, the investigator must assess and document the seriousness, duration, causal relationship to study drug (TACE/sorafenib/other systemic anti-cancer drug), action taken and outcome of the event.

If a pregnancy occurs during the study, although it is not a serious adverse event, it should be reported within the same time limits as a serious adverse event. The result of a pregnancy should be followed carefully and any abnormal result of the mother or baby should be reported.

The documentation of any AE/SAE ends with the completion of the “End of observation” section of the electronic CRF. However, any AE/SAE occurring up to 30 days after the last intake of Sorafenib has to be documented, even if this period goes beyond the end of observation.

As long as the patient has not received any TACE or any other studied treatment, AEs/SAEs do not need to be documented as such in this non-interventional study. However, they are part of the patient’s medical history.

For any serious drug-related AE occurring after study end, the standard procedures that are in place for spontaneous reporting have to be followed.

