### Serious AEs

Any SAE or pregnancy entered into the electronic CRF will be forwarded immediately (within 24 hours of awareness) to the pharmacovigilance country person being responsible for SAE processing. The outcome of all reported SAEs (resolution, death etc.) will be followed up and documented. Where required, investigators might be contacted directly by the pharmacovigilance country person in charge to provide further information.

Submission to the relevant authorities according to national regulations will be done by the sponsor for SAEs occurring under Sorafenib treatment; however, all investigators must obey local legal requirements.

For SAEs that occurred while administering TACE treatment, other systemic anti-cancer drugs or other non-systemic anti-cancer drugs the investigator has to account for and comply with the reporting system of the product's Marketing Authorization Holder within the frame of local laws and regulations as well as other locally applicable laws and regulations.

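### Non-systemic HCC therapy may be recorded with a year-only start date, which does not secure the planned summary of adverse events for each HCC treatment

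*Protocol*

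**What the plan says.** **Where the therapy is recorded.** Table 2 in protocol section 9.3 has an item for "concomitant medication (including non-systemic therapy for HCC"), completed at the initial, follow-up and last visits.

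**Which dates are required.** For that item, section 9.3.6 asks for "Start date (at least year"). The end is recorded as "Stop date or “continued”, with no year-only allowance stated. The entry also carries its purpose, with "Indication: “treatment of HCC” as one option, so HCC entries can be identified.

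**Which treatments have their own exposure record.** Section 9.3.10 lists fields for TACE (date of administration), for sorafenib (start, changes, interruptions, stop) and, under "Information on other systemic treatments to be documented", a start and a stop date. It attaches no year-only allowance to any of these, and it has no block for non-systemic therapy other than TACE.

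**What the analysis needs.** Section 9.7.6 states: "AEs occurred during treatment for HCC also will be summarized for each treatment for HCC".

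**Causality and reporting.** Section 11.2 has the investigator assess "causal relationship to study drug (TACE/sorafenib/other systemic anti-cancer drug"). Section 11.3, on serious events, refers to TACE, "other systemic anti-cancer drugs or other non-systemic anti-cancer drugs the investigator has to account for", and uses the same categories for non-serious adverse drug reactions.

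**The concern.** The summary in section 9.7.6 is defined by time: an event belongs to a treatment if it occurred during it. That requires a start date precise enough to order the event against it. For TACE, sorafenib and other systemic drugs the protocol asks for such dates. For any other non-systemic HCC therapy the minimum is a calendar year, and an analysis plan cannot recover a date that was never collected.

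At stake is the safety output by treatment in a study registered as a post-authorization safety study. Events under a later locoregional therapy could fall outside every treatment period or be counted under TACE or sorafenib.

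A separate and lesser matter is causality. Section 11.2 names three categories, none of them non-systemic, while section 11.3 handles non-systemic anti-cancer drugs as a category of its own. This concerns classification by suspected cause, not the time-based summary, and better dates would not settle it.

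**Working it through.** The plan states no figure on this point, so there is none to reproduce. The check sets the sections against each other and then sizes the date uncertainty.

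**Text comparison**

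| Treatment | Exposure record (9.3.10) | Year-only start allowed | Named in causality list (11.2) |
|---|---|---|---|
| TACE | yes | not stated | yes |
| Sorafenib | yes | not stated | yes |
| Other systemic | yes | not stated | yes |
| Other non-systemic | no; concomitant medication (Table 2) | yes (9.3.6) | no |

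Section 9.7.6 makes no distinction between these rows.

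**Inputs**
- Observation per patient: about 18 months (section 9.2.5), that is 18 × 30.4375 ≈ 548 days.
- Interval between documented status assessments: assumed 6 to 12 weeks (section 9.2.5), that is 42 to 84 days.
- Width of a year-only date: up to 365 days.

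**Step 1, largest uncertainty.** 365 / 548 ≈ 0.67. A bare year can leave the start unknown across two thirds of the observation period.

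**Step 2, trimmed to the patient's own window.** The therapy cannot start before or after observation, so the feasible interval is the overlap of the stated calendar year with that window. For example, a patient observed from 1 July to the end of the next year has 184 feasible days if the first year is entered and 365 if the second is. With first TACE spread evenly over the calendar year and therapy starts spread evenly over the 548 days (both assumptions), the feasible interval averages about 283 days, with median 315 and range 1 to 365.

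**Step 3, compared with visit spacing.** 283 / 84 ≈ 3.4 and 283 / 42 ≈ 6.7. A bare year is thus some three to seven times coarser than the documented visits.

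**Step 4, imputation.** Placing the start at mid-year gives an error of at most about 365 / 2 ≈ 183 days, and of about 365 / 4 ≈ 91 days on average if starts are even over the year. The average error is longer than one assessment interval.

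Steps 1 to 4 apply only to entries where the site gives the year alone and nothing else narrows the start.

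**The case against.** The strongest reply is that the year is a floor, not the usual entry. Section 9.3.6 covers all concomitant medication, including long-standing drugs whose start may be unknown, and nothing stops a site from giving the full date. Other data also help. Section 9.2.5 counts a new treatment decision taken with the patient present as a visit, section 9.3.7 requires day, month and year for visits, and Table 2 makes the decision on further treatment mandatory at each follow-up visit. A therapy started during observation will often arise at a dated visit or lie between two. For a one-day procedure, a full stop date fixes the day. The CRF, data management plan and SAP are not shown and may demand more.

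Much of this stands. A reader might infer that these events can never be dated, or that it can never be known whether the therapy preceded TACE non-eligibility. Neither follows, because both depend on the site entering a bare year with no bracketing information. What remains is that the protocol permits the needed precision without requiring it and does not say that a concomitant entry is tied to a visit.

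A reader might also infer that investigators will attribute such events to TACE, to sorafenib or to nothing. The protocol does not say how they will behave, and other systemic drugs are a third listed option. Nor do sections 11.2 and 11.3 directly contradict each other: the former asks about study drugs, the latter sets reporting routes through the other product's authorization holder. Their lists differ and should be aligned, but that is secondary.

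Finally, each treatment in section 9.7.6 could be read as only those with exposure records in section 9.3.10. If that is meant, the protocol should say so.

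**Conclusion.** The point holds in a limited form. The minimum date rule in section 9.3.6, with no exposure record in section 9.3.10, does not secure the summary that section 9.7.6 plans for every HCC treatment. For entries with only a year, the start is uncertain by up to 12 months within about 18 months of observation, and by less where dated visits or the stop date bracket it. Events then cannot be reliably placed before or during the therapy and may be left unassigned or assigned to another treatment.

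The number of patients concerned is unknown. The protocol states neither how many will receive such therapy nor how often only the year will be entered. A difference between the two cohorts is conceivable but has no support in the document.

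The effect is confined to descriptive safety tables. A reader might extend it to the primary result, but section 9.7.4 defines the cohorts by the sorafenib decision at TACE non-eligibility and measures survival from that time, so this date rule leaves the overall survival comparison and the sample size untouched. It is a cheap improvement to a stated rule.

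**What to change.** 1. In section 9.3.6, require day, month and year for the start, and for the stop once therapy has ended, of every entry whose indication is treatment of HCC. Keep the year-only option for all other entries.
2. Query existing HCC entries with incomplete dates before database lock; Table 1 places the clean database in Q3 2017.
3. Secondarily, reconcile the causality list in section 11.2 with the categories in section 11.3, for example by adding a non-systemic anti-cancer category.

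The cost is a CRF edit check, a possible extra causality option, and some query burden at sites. No additional patient procedure is involved.

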### **9.3.7. Visit date(s)**

Information on visit date(s) at initial visit and each documented follow-up visit includes:

- Date (day, month, year)

### **9.3.8. Disease status summary**

The following criteria will be assessed at initial visit and every follow-up visit:

- lack of portal blood flow (because of portal vein thrombosis, portosystemic anastomoses or hepatofugal flow)
- Patients with lobar or segmental portal vein thrombosis.
- Patients with advanced liver disease (Child–Pugh class B or C)
- Clinical symptoms of end-stage cancer
- Extrahepatic spread (N1, M1)
- ECOG PS  $\geq 1$
- BCLC C or D
- Vascular invasion.
- Two or more consecutive incomplete necrosis (depositions (50%) of lipiodol) are seen by response evaluation CT within the treated tumors at the 4 weeks after adequately performed TACE. (excluded from initial visit)
- Two or more consecutive appearances of a new lesion (recurrence) are seen in the liver by response evaluation CT at the 4 weeks after adequately performed TACE. (excluded from initial visit)
- TACE failure by investigator’s assessment (excluded from initial visit)
- Clinical encephalopathy
- Refractory ascites
- Hepatorenal syndrome
- Extensive tumor with massive replacement of both entire lobes
- Technical contraindications to hepatic intra-arterial treatment
- Renal insufficiency (creatinine  $\geq 2$  mg/dL or CrCl  $< 30$  mL/min)
- Other (to be specified)

### **9.3.9. Tumor assessment**

Patients will be assessed for response to TACE and tumor assessment preferably by mRECIST. In case that an assessment by mRECIST is not possible, because this is not routinely done at the site of the treating physician, also other evaluation criteria can be used. In any case the criteria used have to be documented along with the tumor evaluation and the physician should use the same criteria throughout all tumor evaluations of one patient.

TACE response to most recent TACE will be assessed within 12 weeks after TACE and recorded for each TACE.

Response evaluation will also be done compared to initial TACE. For patients treated with sorafenib, response evaluation compared to initiation of sorafenib will be added.

Tumor assessment will be made at physicians' discretion using CT scan or MRI or equivalent imaging exam, starting from initial TACE.

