### 9.1.2. Secondary endpoint(s)

The secondary endpoints for all patients and the two cohorts of special interest are:

- Overall Survival (OS) from initial TACE is defined as the time interval from the day of the first TACE to death due to any cause. Patients alive at the end of the study will be censored at the last date known to be alive.
- Progression-free survival (PFS) from initial TACE is defined as the time interval measured from the day of the first TACE to documented (radiological or clinical) progression or death, whichever comes first.
- Time to progression (TTP) from initial TACE is defined as the time interval from the day of first TACE to the date of documented progression. Patients without tumor progression at the end of the study will be censored at their last date of tumor evaluation.
- Tumor response to TACE by mRECIST will be evaluated according to the categories “Complete Response”, “Partial Response”, “Stable Disease”, and “Not evaluable” by mRECIST for each TACE.
- Duration of TACE treatment is defined as the time interval from of the day of first TACE to the date of permanent discontinuation of TACE (when an investigator decides TACE is no longer applicable regardless of the reason for discontinuation including death).
- TACE unsuitability will be determined according to the selected guidelines including AASLD, APASL, JSH, EASL-EORTC guidelines ...etc.
- Time to TACE non-eligibility will be determined according to the selected guidelines including AASLD, APASL, JSH, EASL-EORTC guidelines ...etc.
- Deteriorations of liver dysfunction will be evaluated throughout the study. Deteriorations of liver dysfunction are defined as below
  - Deterioration of Child-Pugh score (A5, A6, B7, B8, B9)
  - Liver dysfunction reported as AE or deterioration of AST, ALT or Bilirubin (from Grade1 to Grade 2-5, from Grade 2 to 3-5, Grade 3 to Grade 4 or 5.)
  - Any liver related adverse events or deterioration of liver related events according to CTCAE Version 4.03
  - Change of liver related lab data (AST, ALT, Bilirubin, Alb, INR)

Specific secondary endpoints for patients treated with sorafenib are:

- Overall survival (OS) from initiation of sorafenib is defined as the time interval measured from start date of sorafenib treatment to death due to any cause. Patients alive at the end of study will be censored at the last date known to be alive.

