- Progression-free survival (PFS) from initiation of sorafenib is defined as the time interval measured from the start date of sorafenib treatment to documented (radiological or clinical) progression or death, whichever comes first.
- Time to progression (TTP) from initiation of sorafenib is defined as the time interval from start date of sorafenib treatment to the date of documented progression. Patients without tumor progression at the end of the study will be censored at their last date of tumor evaluation.
- Duration of sorafenib treatment is defined as the time interval from start date of sorafenib treatment to the date of permanent discontinuation of sorafenib treatment (regardless of the reason for discontinuation including death).
- The tumor status at different visits response according to mRECIST will be evaluated according to the categories “Complete Response”, “Partial Response”, “Stable Disease”, “Clinical Progression”, “Radiological Progression”, and “Not evaluable at this visit”. The best overall response will be analyzed providing absolute and relative frequencies of the tumor status categories.
- Incidence of Treatment-emergent Adverse Events (TEAEs) – patients will be monitored for TEAEs using the NCI-CTCAE Version 4.03. Details on the collection, management and reporting of TEAEs can be found in section 11.

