### **9.7.8. Bias, confounding and effect-modifying factors**

As the study aims to compare two non-randomized cohorts of patients as defined in 9.7.4, all factors probably influencing treatment assignment as well as the outcome have to be taken into account to avoid false positive or false negative interpretation of data. It will be tried to control for the effect of confounders using propensity score based methods (see 9.7.4). Possible confounders are:

- Demography (age, gender)
- Etiology (Hepatitis C, Hepatitis B, alcoholic)
- Previous treatment (hepatectomy, number of previous TACE)
- Response to the last TACE
- Barcelona-Clinic Liver Cancer (BCLC) Stage at the time of TACE non-eligibility
- Liver dysfunction: Child-Pugh status at the time of TACE non-eligibility
- Tumor size at the time of TACE non-eligibility
- Vascular invasion at the time of TACE non-eligibility
- Extrahepatic spread at the time of TACE non-eligibility
- Number of lesions at study entry: at the time of TACE non-eligibility
- Physicians' speciality
- Region

A complete list of expected confounders will be added to the SAP.

It is important to note that the propensity score method can only account for confounders that have been measured in the study, but of course not for any unknown or unmeasured confounders. As a consequence, it cannot be ensured that the resulting hazard ratio estimation is completely free of bias and thus the results have to be interpreted with care.

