## 16.5. RECIST Criteria

### Modified RECIST (mRECIST)

Response and progression should preferably be evaluated in this study using a modified version of RECIST version 1.1, which combines quantitative assessment of a set of lesions using unidimensional measurements with qualitative assessment of all other lesions (Eisenhauer EA et al.; New response evaluation criteria in solid tumours: Revised RECIST guideline (version 1.1). EJC 2009 45:228-247).

The modifications introduced for the assessment of intrahepatic lesions are based on the modified RECIST criteria published in 2010 for the assessment of hepatocellular carcinoma (Lencioni R and Llovet JM; Modified RECIST (mRECIST) Assessment for Hepatocellular Carcinoma. Sem Liver Dis 2010 30;1:52-60).

Results from a number of previous clinical studies in HCC have demonstrated that RECIST does not adequately capture the extent of tumor necrosis induced by interventional therapies or new molecular targeting drugs. Only viable tumor, assessed by properly designed CT or MRI studies, should be included in the tumor burden, and viable tumor should be defined as uptake of contrast agent in the arterial phase of dynamic imaging studies. Consequently, a modification of RECIST was first proposed by a panel of experts, and further expanded. This proposal is based on the fact that the diameter of the target lesions with viable tumor tissue should be the basis of measurements for intrahepatic lesions. In addition, there are specific modifications of the original criteria regarding the assessment of vascular invasion, lymph nodes, ascites, pleural effusion, and new lesions. (Llovet JM, et al.; Panel of Experts in HCC-Design Clinical Trials: Design and Endpoints of Clinical Trials in Hepatocellular Carcinoma. J Natl Cancer Inst. 2008 May 21;100(10):698-711)

The expert panel has adopted the concept of viable tumor endorsed by European Association for the Study of the Liver (EASL) and proposed amendments (Llovet JM, et al. 2008) to RECIST in the determination of tumor response for HCC, which have been incorporated into the criteria in this trial as described herein.

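### Response endpoints are defined by mRECIST alone while sites may read tumors by other, unlisted criteria, and PFS and TTP take progression on whatever scale was used

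*Protocol*

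**What the plan says.** Section 9.1.2 ties two response endpoints to one scale. For TACE: "Tumor response to TACE by mRECIST will be evaluated according to the categories" (the list of categories follows). For sorafenib: "The tumor status at different visits response according to mRECIST will be evaluated according to the categories", with best overall response taken from those categories.

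Section 9.3.9 prefers mRECIST but opens a second route for sites where mRECIST is not part of normal practice. There, "also other evaluation criteria can be used". It names no permitted alternatives. It does add a safeguard: "the criteria used have to be documented along with the tumor evaluation and the physician should use the same criteria throughout all tumor evaluations".

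PFS in 9.1.2 runs to "documented (radiological or clinical) progression or death, whichever comes first". TTP runs to documented progression. Neither names response criteria.

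Annex 16.5 gives the reason for preferring mRECIST: "RECIST does not adequately capture the extent of tumor necrosis induced by interventional therapies". Sections 9.7.1 and 9.7.7 plan analyses by region, including response to each TACE by procedure and region. The abstract extends the propensity score comparison of the two cohorts to secondary endpoints where applicable.

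**The concern.** The endpoint definitions and the assessment rule do not fit together. A patient at a site that does not use mRECIST has valid readings under 9.3.9. Section 9.1.2 does not say whether those readings enter the response endpoints, are left out, or are shown apart. For PFS and TTP the text is less open: any documented progression counts, so following it places readings from different scales in one analysis.

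This matters because the scale is not spread at random over patients. It follows the habit of the site and so may vary with region. Sorafenib use may vary with site and region too. A difference in PFS or TTP between the early-sorafenib cohort and the other cohort, or in TACE response between regions, could then be partly a difference in how tumors were measured.

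**Working it through.** **1. The plan's own figures.** The protocol attaches no figure to the choice of criteria. Its one power statement (section 9.5) concerns OS. With medians of 9 and 12 months, 18 months of accrual, 36 months in total and exponential survival, the death probabilities are 0.865 and 0.780. Expected deaths are 250 × (0.865 + 0.780) = 411. With a hazard ratio of 9/12 = 0.75, power is Φ(√411/2 × |ln 0.75| − 1.96) = Φ(0.96) = 83%, as stated. Response criteria do not enter this calculation.

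**2. Definitions side by side.**

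| Endpoint | Scale in 9.1.2 | Readings admitted by 9.3.9 | Result |
|---|---|---|---|
| Response to each TACE | mRECIST only | mRECIST or other | handling of other readings not stated |
| Tumor status and best response, sorafenib | mRECIST only | mRECIST or other | handling of other readings not stated |
| PFS | none named; clinical progression and death also count | mRECIST or other | scales combined as written |
| TTP | none named | mRECIST or other | scales combined as written |

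**3. Can the scales disagree on one scan?** The thresholds are those of Annex 16.5: partial response is a decrease of at least 30% from baseline; progression is an increase of at least 20% from the smallest sum, and at least 5 mm. mRECIST measures the enhancing part of a liver lesion. A RECIST-type reading is taken here as the diameter of the whole lesion. The constructed patient has one 60 mm lesion, fully enhancing at baseline, whose outer diameter does not change.

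- After TACE, 20 mm still enhances. mRECIST: (20 − 60)/60 = −67%, partial response. Whole lesion: (60 − 60)/60 = 0%, stable disease.
- Later the enhancing part grows to 26 mm. mRECIST: (26 − 20)/20 = +30% and +6 mm, progression. Whole lesion: 0%, still stable disease.

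On the second scan only one scale records an event. If nothing else triggers progression, the other scale dates it at least one assessment later. Section 9.3 (note to Table 2) assumes 6 to 12 weeks between tumor assessments.

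**4. What sets the size.** Suppose two groups have identical disease. The artefact in the pooled response rate is then

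(difference in share read by mRECIST) × (difference in response rate between the scales).

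The protocol gives neither factor. Purely as assumed inputs, take 80% and 40% mRECIST use, with response 50% by mRECIST and 15% to 30% by whole-lesion criteria:

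- with 15%: 0.8 × 50 + 0.2 × 15 = 43% against 0.4 × 50 + 0.6 × 15 = 29%, a gap of 14 points;
- with 30%: 0.8 × 50 + 0.2 × 30 = 46% against 0.4 × 50 + 0.6 × 30 = 38%, a gap of 8 points.

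With equal mRECIST use in both groups the gap is zero. These figures show how the mechanism works and do not estimate its size in this study.

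**The case against.** Allowing other criteria is deliberate and reasonable. Section 5.1 gives the reason, and section 10.1 rules out additional diagnostic procedures in this non-interventional study. The protocol also secures what could not be recovered later: the criteria are recorded and should stay constant within a patient, so mixing arises between patients and sites. Section 9.7.1 leaves statistical detail to the SAP, and the abstract calls the analyses explorative and descriptive. All of this stands, and it limits the weight of the point. It does not settle what the endpoints in 9.1.2 are, because the protocol fixes those definitions itself and they conflict with 9.3.9.

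Four stronger readings are tempting and are not supported:

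- *That the plan pools all readings under the mRECIST label.* No section orders this. Taken literally, 9.1.2 could equally limit those endpoints to mRECIST readings. Combination follows from the text only for PFS and TTP.
- *That the protocol says every other scale disagrees with mRECIST.* Annex 16.5 criticises RECIST. It also notes that EASL endorsed the viable-tumor concept.
- *That the OS comparison is biased through the covariate "Response to the last TACE".* The score models the physician's decision, and the local reading is what could have driven it. Region and physician speciality are already listed in 9.7.8, and the full confounder list is left to the SAP.
- *That the artefact is 8 to 14 points.* That range comes entirely from assumed inputs.

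PFS also counts death and clinical progression, and under Annex 16.5 new lesions count as progression whatever the target response. Both dilute any effect of scale on progression dates.

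**Conclusion.** Sections 9.1.2 and 9.3.9 conflict and should be reconciled. The response endpoints are defined on a scale that some patients need not be read on, and PFS and TTP as written combine scales. By the protocol's own account, one of the likely alternatives, RECIST, performs poorly after the treatment every analyzed patient receives. RECIST-type and mRECIST readings can therefore give different categories and progression dates for the same scan. Cohort comparisons of PFS and TTP and regional response summaries can partly reflect the scale.

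Neither the size nor the direction can be derived from the protocol. Both depend on how many patients are read by other criteria, how many of those criteria measure the whole lesion, and how their use divides between cohorts and regions. The worked example assumes a single lesion of unchanged outer diameter. The primary OS endpoint is not directly affected. This is a correction of secondary endpoints that should be made; it is no threat to the main comparison.

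**What to change.** In 9.1.2 and 9.7.5, state that the response endpoints named by mRECIST include only patients read by mRECIST, and that patients read by other criteria are tabulated separately.

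For PFS and TTP, stratify the cohort comparison by criteria used (mRECIST against other). If crossing this with the propensity strata leaves sparse cells, repeat the comparison in mRECIST-read patients as a sensitivity analysis instead. Sparse cells are a realistic risk: with the 500 patients of section 9.5 and an assumed five strata, two criteria groups give ten cells averaging 500/10 = 50 patients, both cohorts together, and uneven use would make some cells smaller.

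No new data are needed, since 9.3.9 already requires the criteria to be recorded with each evaluation. The cost is wording, fewer patients in the mRECIST tables and somewhat wider intervals. Entering the criteria alongside the response covariate in the propensity score is optional, and this point does not depend on it.
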